In this laboratory-based within-subjects study participants will attend two sessions. Before both sessions, participants will be asked to abstain from smoking overnight and until the end of the testing day. For one session, participants will be asked to apply an active nicotine patch 30 minutes before the behavioural assessment and use a nicotine nasal spray *ad libitum*. For the other session participants will be asked to apply a placebo patch and will receive placebo nasal spray. Participants will be blinded as to which treatment they receive. The order of the sessions will be counterbalanced across participants.

On each testing day, the behavioural assessments will be completed in the morning, with the order of the cognitive computer-tasks counterbalanced across participants and fixed within participants. After testing, participants will be provided with an Android mobile device to measure craving for another six hours, using a specifically programmed app. The assessment of craving can be done remotely, so participants can leave the testing site. After six hours participants will be asked to return the mobile device and the nasal spray to the researcher, have their abstinence confirmed via breath test and their patch removed.

Study Site

School of Experimental Psychology, University of Bristol, [name], United Kingdom.

Participants and Recruitment

We will recruit individuals aged 18 to 60 years, who are regular smokers from the staff and students of the University of Bristol and from the general population.

Participants will be recruited by existing email lists, posters, flyer advertisement, and by word of mouth. After contacting the research coordinator and reading the study information sheet, participants will complete an initial online screening form. Those who meet the inclusion and exclusion criteria will be contacted by the research coordinator to arrange a testing session. Participants will be reimbursed £80 for their

time and expenses.

Inclusion criteria

- 18-60 years old.
- smoke at least 5 cigarettes per day.
- smoke first cigarette within one hour of waking.
- smoking for at least 6 months.
- English as first language (or equivalent level of fluency).
- visual acuity within normal limits.

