- willingness to abstain from smoking for about 20 hrs on two occasions, once with using nicotine patch and nasal spray and once using placebo nicotine patch and nasal spray without being made aware of the order of the conditions at any point of the study.
- if female: willingness to take a pregnancy test before each study session.

Exclusion criteria

- currently taking any psychoactive medication
- actively trying to give up smoking
- history of substance/alcohol misuse or dependence (other than nicotine or cannabis)
- if female: pregnant, breast feeding or trying to conceive
- having extensive dermatitis/other skin disorder that precludes patch use
- having had acute coronary syndrome or a stroke within the past three weeks
- allergic to any component of the nicotine replacement therapy patch or nasal spray

Sample size determination

We will require 70 participants to achieve 80% power and an alpha-level of 0.5, in order to detect the smallest effect size indicated in our recent meta-analysis ($d = 0.34$ for the delay-discounting task) ([name] et al., under review). The smallest effect size available was used in order to provide the most conservative sample size estimate. For the cognitive task with the largest effect size ($d = 0.59$ for the n-back task), a sample size of 25 participants would suffice (Mendrek et al., 2006).

Withdrawal of participants

Participants will be informed that they are able to withdraw from the study at any time. In the case of an adverse event, that is any unforeseen or serious reaction to the procedure or the NRT products, participants will be given full reimbursement of £80. In the case of the participant not tolerating the NRT product by displaying any of the harmless side effects described below, participants will be reimbursed £35 if this occurs in the first session, and £80 if this occurs in the second session. In the case of the researcher being unable to track the eyes of the participant they will be reimbursed a monetary amount that is commensurate with the time they have spent in the laboratory (e.g., stopping half way through the first session would result in a reimbursement of 25%).

Randomisation

The order of sessions (placebo, NRT) will be counterbalanced. The order of the cognitive tasks during the laboratory session will be randomized across participants, and fixed within participants.

Measures and Materials

- Working memory performance (number of commission errors) as measured by the n-back task

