Indifference points will be derived and will be used to calculate area under the curve (AUC), using the following equation: $(x_2 - x_1)[y_1 + y_2/2]$, where x_2 and x_1 represent successive delays to receiving the standard and y_1 and y_2 the indifference point values associated with these delays. Smaller AUC values indicate greater discounting and impulsive choice (Mitchell 1999, Ashare and Hawk Jr 2012). The principal statistical analysis will be a one-way ANOVA of AUC values, with nicotine (active, placebo) as a within-subjects factor.

N-back task

The principal statistical analysis will be a one-way ANOVA of hit rates, with nicotine (active, placebo) as a within-subjects factor.

Go/no-go task

The principal statistical analysis will be a one-way ANOVA of commission error data, with nicotine (active, placebo) as a within-subjects factor.

Dot-probe task

The principal statistical analysis will be a 2 by 2 repeated measures ANOVA of eye movement dwell time data, with picture type (smoking, neutral) and nicotine (active, placebo) as within-subjects factors.

Ecological momentary assessment

Cigarette craving will be analysed using Generalized Estimation Equations in order to determine differences between the active and placebo NRT conditions.

Ethical Considerations and Informed Consent

Ethics approval has been obtained from the Faculty of Science Research Ethics Committee at the University of Bristol. The study will be conducted according to the revised Declaration of Helsinki (2013) and the 1996 ICH Guidelines for Good Clinical Practice E6 (R1). The investigator will explain the nature, purpose and risks of the study to the participant. The participant will receive the information sheet in

advance of the study session. There will be no time restriction on how long participants take to respond, with the exception that participants who respond after all study places have been filled will not be offered a place on the study. Therefore, participants will be given sufficient time to read the information and consider any implications, and to raise any questions with the investigators prior to making a decision to participate. On arrival at the study session participants will be given the opportunity to read the information sheet again and ask the investigator any questions. Written consent will then be obtained. Participants will be informed that they are free to withdraw at any time.

Safety

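### Session order is counterbalanced, but the four principal ANOVAs have no session or order term, so any shift between sessions is counted as error and power is lost

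*Protocol*

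**What the plan says.** Under Study Design the protocol sets out a two-period crossover: "In this laboratory-based within-subjects study participants will attend two sessions", one with active and one with placebo NRT. It adds: "The order of the sessions will be counterbalanced across participants". The Randomisation section repeats this: "The order of sessions (placebo, NRT) will be counterbalanced". Under Procedures the sessions are at least a week apart, and both include the four cognitive tasks.

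The Statistical Plan names the factors of each principal analysis. For delay discounting: "The principal statistical analysis will be a one-way ANOVA of AUC values, with nicotine (active, placebo) as a within-subjects factor". The n-back (hit rates) and go/no-go (commission errors) analyses have the same single factor. The dot-probe analysis is a 2 by 2 ANOVA with picture type and nicotine. None of the four has a session, period or order term. For craving, the plan names only the method (GEE) and the active-placebo contrast.

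The sample size section states: "We will require 70 participants to achieve 80% power and an alpha-level of 0.5", for the smallest effect size, d = 0.34. It makes no allowance for drop-out. The section on withdrawal foresees stopping for NRT intolerance in either session: "participants will be reimbursed £35 if this occurs in the first session, and £80 if this occurs in the second session".

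**The concern.** Counterbalancing stops a session effect from being confused with treatment. It does not remove that effect from the data. Each participant's active-minus-placebo difference contains the session shift, with a plus sign if active came second and a minus sign if it came first. An ANOVA with nicotine as its only factor treats this systematic spread as random error. The design pays for control of order, and the analysis then leaves the gain in precision unused.

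Two things are at stake. The first is power: the stated sample size gives 80% with nothing to spare. The second is conditional: if the two orders end with unequal numbers of completers, the plus and minus shifts no longer cancel and the unadjusted estimate is biased.

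**Working it through.** **Inputs.** N = 70, d = 0.34 and 80% power are from the sample size section, as are d = 0.59 and N = 25 for the n-back task. The 35:35 split is an assumption; the protocol says only that order is counterbalanced. The shift p (session 2 minus session 1, in SDs of the paired difference within an order) is also assumed, over 0 to 1.

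**The plan's own figure.** A one-way within-subjects ANOVA with two levels is a paired t-test. With the noncentral t and two-sided alpha 0.05, N = 70 gives power 0.801 at d = 0.34, and N = 25 gives 0.808 at d = 0.59. Both planned sizes are reproduced. The printed alpha of 0.5 would need only 19 participants for d = 0.34 (two-sided), so 0.05 is used here; that misprint is a separate matter.

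**Model.** For participant i, D_i = τ + s_i·p + e_i, with s_i = +1 if active is second and −1 if it is first, and e_i of SD 1. Let n1 and n2 be the completers in the two orders and n = n1 + n2.

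- Mean of D without an order term: τ + p(n1 − n2)/n. At 35:35 the second part is zero, so the estimate is unbiased.
- Error variance at 35:35 without an order term: 1 + p² to a close approximation, that is 1.0625, 1.25 and 1.5625 at p = 0.25, 0.5 and 0.75.
- With order fixed at 35:35, the shift cancels from the mean and inflates only the estimated SD. The residual sum of squares is noncentral chi-square with 69 df and noncentrality 70p². The sampling variance of the mean stays at 1/70.

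**Result at 35:35, τ = 0.34** (type I error at τ = 0):

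| p | Power, no order term | Power, with term | Type I error, no order term |
|---|---|---|---|
| 0 | 0.80 | 0.80 | 0.050 |
| 0.25 | 0.78 | 0.80 | 0.043 |
| 0.5 | 0.73 | 0.80 | 0.029 |
| 0.75 | 0.64 | 0.80 | 0.014 |
| 1.0 | 0.51 | 0.80 | 0.006 |

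Simulation agrees to within about 0.01. Adjusting costs one degree of freedom (68 instead of 69), and power is 0.801 either way when p = 0.

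**Unequal completers.** Bias = p(n1 − n2)/n. Suppose seven of 70 are lost. From a 35:35 start the most unequal result is 35 and 28, and at p = 0.5 the bias is 0.5 × 7/63 = 0.056 SD, or 0.056/0.34 = 16% of the target effect. Unadjusted type I error is then about 0.044, still below 5%. If ten were lost, all from one order (35 and 25), the bias at p = 0.5 would be 0.5 × 10/60 = 0.083 SD, or 25%, with type I error about 0.064. With the order term the estimate is unbiased in each case and type I error is about 0.05.

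**The case against.** The strongest reply is that the planned test is valid. With balanced orders the estimate is unbiased and the test errs on the safe side. That stands: the loss is of power, and a reader should not infer a false-positive problem from the missing term alone.

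A reader might also infer that NRT intolerance, being commoner on active treatment, must unbalance the orders. The documents do not support this. Each order contains exactly one active session, so an equal intolerance rate that broke the pair in either session would cost both orders equally. A further asymmetry is needed. One is possible under the procedures: the patch stays on and the spray stays with the participant for six hours after the tasks. Intolerance late in session 1 could prevent session 2, whereas late in session 2 the cognitive data are already complete. That would remove active-first participants preferentially, but nothing shows that it will happen. The payment rule shows only that withdrawal is foreseen in either session. If seven losses were unrelated to order, a 35/28 split would have a probability of about 1%. The mean absolute imbalance would be 2.1/63, so the bias at p = 0.5 would be 0.5 × 2.1/63 = 0.017 SD, or 5% of 0.34.

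Nor does the protocol establish a practice effect. It is most plausible for n-back and go/no-go, although their practice trials may reduce it. It is less obvious for hypothetical money choices, and it touches the dot-probe interaction only if the smoking-neutral difference itself shifts between sessions.

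Finally, if the SD behind d = 0.34 already contained order variance, N = 70 keeps 80% power without the term, and adding it would raise power above that.

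The reply that model terms may be left to a SAP does not meet the point for the ANOVAs, because the protocol names their factors. It does hold for craving: the GEE terms are not listed, so no omission can be claimed there.

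**Conclusion.** The point holds for the four analyses labelled principal. Followed as written, they count any session shift as error. With 35:35 orders and d = 0.34 standardised by the within-order SD, power falls from 0.80 to about 0.78, 0.73 or 0.64 at an assumed shift of 0.25, 0.5 or 0.75 SD. With no shift, nothing is lost. Bias is a secondary and conditional risk that needs both a session effect and unequal completers: 16% of the target effect at 35/28 and p = 0.5, and less under more even losses. This is not a threat to the validity of the balanced comparison. It is an avoidable loss of precision, and the remedy costs almost nothing, so the change should be made.

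**What to change.** Add session number (period) to each principal model, in one of two ways:

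- A linear mixed model per outcome with fixed effects for nicotine and session and a random participant effect, plus picture type and its interaction with nicotine for the dot-probe. This can also keep participants with one valid session. For the dot-probe, let session interact with picture type too, since only that part of a session shift reaches the picture-by-nicotine term.
- For completers only, a mixed ANOVA with order as a between-subjects factor, where the nicotine-by-order term carries the session shift. The nicotine effect should weight the two orders equally.

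The two are not interchangeable when drop-out occurs, because the ANOVA discards anyone with a single session. State which is chosen. Report the number of completers by order in either case.

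For the craving GEE, naming session number among the terms is a suggestion, not a correction.

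The cost is a change of wording and one degree of freedom. No new data are needed, and N = 70 stands.

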School of Experimental Psychology
[name]
[name]
United Kingdom

[name] t.
[name] f.
[contact]
www.bristol.ac.uk

STUDY PROTOCOL

Are cognitive deficits associated with tobacco abstinence mediated by nicotine withdrawal?

[name], [name], [name], [name], [name],
[name]

Background

Smokers report cognitive deficits following tobacco withdrawal, which may contribute to the withdrawal syndrome and subsequent relapse. However, it is unclear whether these deficits are primarily due to the effects of nicotine withdrawal or other mechanisms such as expectancies about the effects of abstaining or the loss of sensorimotor stimulation.

In a systematic review of the literature we identified several cognitive tasks sensitive to a period of acute abstinence ([name] et al., under review). We now wish to determine whether these effects are indeed mediated via nicotine withdrawal. We will do this by comparing task performance of abstinent smokers receiving nicotine replacement therapy (NRT) with abstinent smokers receiving placebo NRT. We expect that performance of abstinent smokers receiving NRT will be different (and more similar to performance of satiated smokers) than performance of abstinent smokers receiving placebo NRT.

Since nicotine withdrawal is known to be dynamic and complex, and fluctuates over time, it is not well captured by a single assessment (Hughes 2007, Bedi, Preston et al. 2011, Adams and [name] 2013). We will use ecological momentary assessment to measure craving of participants via an Android mobile device at several time points over the course of a single day, as participants are in their natural environment.

Study Objective and Hypotheses

We propose to examine the effects of nicotine delivered via NRT on cognition and craving in acutely abstinent smokers. The principal research question to be addressed is:

Are changes in cognitive performance and craving levels due to acute tobacco abstinence mediated by nicotine withdrawal?

We hypothesize that abstinent smokers receiving active NRT will display less impairment in cognitive task performance than abstinent smokers who receive placebo NRT. We also hypothesise that craving assessed via EMA will be higher in abstinent smokers receiving placebo than in abstinent smokers receiving NRT.

Study Design

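### Four task analyses are each called principal for one pooled cognitive hypothesis, with no ranking or combining rule, and N = 70 allows for only one unadjusted test

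*Protocol*

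**What the plan says.** Study Objective and Hypotheses poses a single principal question: "Are changes in cognitive performance and craving levels due to acute tobacco abstinence mediated by nicotine withdrawal". Two hypotheses follow. The first pools the tasks and predicts less impairment in cognitive performance on active NRT. The second, introduced separately, concerns craving measured by ecological momentary assessment (EMA).

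The Statistical Plan then uses the word principal four times, once under each task heading:

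- delay discounting: within-subjects ANOVA of AUC
- n-back: within-subjects ANOVA of hit rates
- go/no-go: "The principal statistical analysis will be a one-way ANOVA of commission error data"
- dot-probe: "The principal statistical analysis will be a 2 by 2 repeated measures ANOVA of eye movement dwell time data"

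Craving gets a generalised estimating equations analysis that is not called principal. The protocol gives no order among the tasks and no rule for what pattern of results answers the question on cognition.

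Sample size determination says "We will require 70 participants to achieve 80% power and an alpha-level of 0.5". The target is the lowest effect found in the investigators' own meta-analysis, which is d = 0.34 for delay discounting. For n-back (d = 0.59), "a sample size of 25 participants would suffice".

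**The concern.** A pooled hypothesis tested by four analyses of equal standing needs a rule: all must succeed, any one suffices, one is primary, or each task is reported for itself. The protocol chooses none of these. A reader who sees one significant task out of four cannot tell whether the cognitive hypothesis was supported as planned.

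The gap also affects the sample size. The number of participants was fixed with the whole of alpha spent on a single test. If the four tasks are later handled as a family, the stated 80% power for the smallest effect no longer describes the test that supports the claim.

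**Working it through.** **Inputs.** From the protocol: N = 70 at d = 0.34, N = 25 at d = 0.59, 80% power, two sessions per participant (so a paired contrast), four analyses labelled principal. Not given: sidedness, a significance level for each analysis, and the correlation between tasks. Alpha is printed as 0.5.

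**Step 1: reproduce the sample sizes.** For a paired t-test, power comes from the noncentral t distribution with n − 1 degrees of freedom and noncentrality d√n.

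- d = 0.34, n = 70: noncentrality 0.34 × √70 = 2.84. At two-sided 0.05 power is 80.1%, and 70 is the smallest n that reaches 80%.
- d = 0.59, n = 25: noncentrality 0.59 × 5 = 2.95. At two-sided 0.05 power is 80.8%, and 25 is the smallest n.

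The alternatives tried do not match:

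| Setting | n for d = 0.34 | n for d = 0.59 |
|---|---|---|
| two-sided 0.05 | 70 | 25 |
| one-sided 0.05 | 55 | 20 |
| two-sided 0.5 (as printed) | 19 | 7 |
| one-sided 0.5 | 7 | 3 |
| two-sided 0.0125 (0.05/4) | 100 | 36 |

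Both published numbers therefore point to an unadjusted two-sided 0.05 for one task at a time. The rest of this check uses 0.05 on that inference.

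**Step 2: chance of at least one false positive among four tests.** With independent tests at 0.05 each, 1 − 0.95⁴ = 1 − 0.8145 = 18.5%.

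The same people perform all four tasks, so positive correlation is likely. The protocol gives no value. Simulating four two-sided z-tests with a common assumed correlation (1,000,000 draws) gives:

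| Assumed correlation | At least one false positive |
|---|---|
| 0.3 | 17.4% |
| 0.5 | 15.6% |
| 0.7 | 13.1% |
| 0.9 | 9.4% |

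This counts one test per task. The 2 by 2 dot-probe ANOVA produces three F-tests (two main effects and the interaction), and the protocol does not say which is the principal one. The count of four assumes that one of them is chosen in advance.

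**Step 3: effect of an adjustment on power.** Holm's procedure compares the smallest of four p-values with 0.05/4 = 0.0125. At that level, d = 0.34 with n = 70 has 61% power; 80% power would need n = 100. The 61% is the least favourable case, because later Holm steps use larger thresholds. At the n-back effect of 0.59, 80% power at 0.0125 needs only 36 participants, so N = 70 is ample there.

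**The case against.** **Principal may mean the main analysis of that task.** Each use stands under its own task heading, and some tasks record more than one measure (dwell time and reaction times for the dot-probe). This is a fair reading, and the protocol does prespecify a variable and a model for every task. It does not remove the gap: the cognitive hypothesis is pooled, and nothing says how four task-level results bear on it.

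**An adjustment may be in a statistical analysis plan that is not shown.** True, and the absence of an adjustment method is not the point. The protocol itself fixes the four labels and the sample size. A later adjustment would alter the power that the protocol states.

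**A reader might infer that the trial runs at about a 20% error rate in place of a promised 5%.** The documents do not support this. No any-one-wins rule is written, no 5% overall rate is claimed, no level is given for the individual analyses, and 0.05 is itself inferred.

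**A reader might add craving as a fifth test**, giving 1 − 0.95⁵ = 22.6%. The principal question does mention craving, but craving has its own hypothesis and its analysis is not called principal. It does not belong in the same family.

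**A reader might take delay discounting as the intended primary outcome because it sets N.** The protocol used it only because its effect was the smallest available, as the conservative choice. That does not make it the main outcome.

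**Nor does the protocol indicate that only a favourable task would be reported.** That is a possibility left open, not something the text shows.

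**Conclusion.** The point holds in a limited form. The protocol sets four principal analyses against one pooled cognitive hypothesis without a ranking or a combining rule, and its sample size leaves no room for more than one unadjusted test. If any single significant task is taken as a yes on cognition, the chance of at least one false positive is at most about 18.5%, about 16% at a correlation of 0.5 and about 9% at 0.9. These figures rest on four assumptions: 0.05 two-sided per test, one test per task, the correlations shown, and that decision rule. Over the correlations shown, the rate stays well above 5%, so the rule is worth settling before data are seen.

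**What to change.** In the Statistical Plan, treat the four task analyses as one family. Report Holm-adjusted p-values next to the unadjusted ones and base any overall claim about cognition on the adjusted values. Say which dot-probe F-test enters the family. State that EMA craving is a separate hypothesis.

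In Sample size determination, correct or explain the printed alpha. State that 80% power for delay discounting is per task at unadjusted two-sided 0.05, and is about 61% at the strictest Holm step (0.0125).

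Alternatively, the investigators may name one task as the single primary before data are seen and label the other three secondary. No overall claim may then rest on a secondary result alone. That condition matters: a primary at 0.05 plus ungated Holm over three secondaries still gives 1 − 0.95 × (1 − 0.05/3)³ = 9.7% for at least one false positive under independence.

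The cost is wording and a little extra analysis. The downside is a stricter threshold per task and a less favourable stated power for the smallest effect.
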